### 3.2.23 Time to flare

The time to flare will be defined as follows:

- For subjects who meet the criteria for flare, the flare date will be defined as:
  - For subjects who first meet the criterion “ASDAS  $\geq 2.1$  at 2 consecutive visits”, the date of the second ASDAS score will be considered the flare date.
  - For subjects who first meet the criterion “ASDAS  $> 3.5$  at any visit”, the date of the corresponding ASDAS score will be considered the flare date.
  - The date of the ASDAS score is defined as the date the corresponding BASDAI/PtGADA assessments were performed and the CRP sample(s) was (were) collected. If the assessments were not performed on the same day, a conservative approach will be used, and the latest day will be taken as calculated ASDAS day.
- Subjects who discontinue the study without Withdrawal Visit will be treated as having experienced a flare at the next planned ASDAS visit. The final available ASDAS score date + 32 (4 Weeks + visit window) will be used as flare date. If Week 48 or Week 50 are last ASDAS visits, Week 48/Week 50 ASDAS date + 18. (2 weeks + visit window) will be used as flare date.
- Subjects who discontinue the study will be treated as having experienced a flare at the date of their withdrawal visit, if the last ASDAS visit date is not equal with the withdrawal date. If the withdrawal date is equal to the last ASDAS visit date, the same approach as for subject without Withdrawal Visit will be used for deriving the flare date.
- Subjects with missing ASDAS scores at 2 or more consecutive visits will be treated as having experienced a flare at the date of the second visit where the ASDAS score is missing, irrespective of whether the subject meets the flare criteria at a later time point.
  - If the date of the second missing ASDAS visit is available, the date of the visit will be used.
  - If the date of the second missing ASDAS visit is not available, the last ASDAS date + 60 (8 weeks + visit window) will be used as flare date. If Week 48 is the last ASDAS visits, Week 48 ASDAS date + 32. (4 weeks + visit window) will be used as flare date. If Week 50 is the last ASDAS visits, Week 50 ASDAS date + 46. (6 weeks + visit window) will be used as flare date.
- For subjects who complete the study without meeting the criteria for flare, the censored date will be the last possible date of the event, i.e. Week 96.

The time to flare will be calculated in days as the difference between the two dates (date of flare or censoring date – date of randomization into Part B+ 1).

Sensitivity analyses will be conducted using different approaches for definition of time to flare. These approaches are described hereafter.

#### Observed case

Using this approach, a subject will be considered to have experienced a flare only if a subject has an ASDAS  $\geq 2.1$  at 2 consecutive visits or an ASDAS  $> 3.5$  at any visit during Part B up until Week 92.

Consequently, unlike for the main approach, subjects who discontinue the study will be censored at the date of their Withdrawal Visit and subjects with missing ASDAS scores at 2 or more consecutive visits will be censored at the date of the second visit where the ASDAS score is missing. In case a subject has missing ASDAS scores at 2 or more consecutive visits and meets the flare criteria at a later time point, the subject will be considered to have experienced a flare and the flare date will be defined as described earlier in this section.

Only the subjects with at least one ASDAS score available at any post-baseline visit during Part B will be evaluable using this approach.

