### **3.2.22 Flare**

A subject is considered to have experienced a flare if a subject has an ASDAS  $\geq 2.1$  at 2 consecutive visits or an ASDAS  $>3.5$  at any visit during Part B up until Week 96.

If a subject has an intermittent missing ASDAS score (ie, a missing value at 1 visit but non-missing values at the previous and subsequent visit), then the missing value will be ignored and the occurrence of a flare will be based on the 2 available values.

If the ASDAS score is missing at 2 or more consecutive visits, then the subject will be considered to have experienced a flare (even if ASDAS scores are available after the missed visits).

There is also the possibility to report one unscheduled ASDAS between two scheduled ASDAS assessments. The same rules as for the scheduled ASDAS apply for the unscheduled ASDAS.

The unscheduled ASDAS will be taken into account for flare calculation for two consecutive visits if there are more than 13 calendar days between two consecutive ASDAS calculated dates.

If the ASDAS score is missing at 2 scheduled visits and unscheduled ASDAS entry present in between and not larger than 3.5, then the subject will not be considered to have experienced a flare.

Occurrence of a flare will be based solely on the observed ASDAS values and will not take into account any imputation of ASDAS. Occurrence of a flare will be determined based on the actual

data entered into the eCRF for the individual ASDAS components, not based on data from the interactive voice or web response system (IXRS).

If a subject prematurely withdraws from Part B at any point for any reason, then the subject will be considered to have experienced a flare.

If a subject was incorrectly identified as flared at any point in Part B due to late data entry in IXRS and went to escape Part B, then the subject will be considered to have experienced a flare.

Sensitivity analyses will be conducted using different approaches for definition of flare. These approaches are described hereafter.

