**Table 3.3: Flare Definition and Time to Flare**

Reason for flare	Event/Censoring day	Non-responder imputation	Observed Case	Alternative handling of premature withdrawal
ASDAS >=2.1 at 2 consecutive visits	Day of 2nd ASDAS	Event	Event	Event
ASDAS >3.5	Day of ASDAS	Event	Event	Event
Subject with Missing ASDAS at two consecutive visits	Planned date for the 2nd ASDAS visit	Event	Censored	Event
Subject discontinued study during Part B due to AE or Lack of efficacy	Day of discontinuation not equal ASDAS visit	Event	Censored	Event
Subject discontinued study during Part B due to other reason	Day of discontinuation not equal ASDAS visit	Event	Censored	Censored
No Flare (completed Part B)	Week 96	Censored	Censored	Censored
Incorrectly 'flared' due to delay in data entry	2nd ASDAS visit or planned date for the 2nd ASDAS visit if missing	Event	Censored	Censored

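### The observed-case time-to-flare rule censors a subject at a two-visit ASDAS gap unless a flare is seen later, so its Kaplan-Meier flare percentages are biased upward, probably by a small amount

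*SAP*

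**What the plan says.** Section 3.2.23 of the SAP defines a sensitivity version of time to flare called the observed case. The event is defined by ASDAS alone: "a subject will be considered to have experienced a flare only if a subject has an ASDAS" at or above the stated thresholds. Missing data are not an event here, unlike in the main approach. Instead, "subjects with missing ASDAS scores at 2 or more consecutive visits will be censored at the date of the second visit" with a missing score.

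The next sentence makes one exception. If a subject with such a gap later "meets the flare criteria at a later time point, the subject will be considered to have experienced a flare". For the date of that event the text only refers back: "the flare date will be defined as described earlier in this section". There is no matching sentence for a subject who resumes ASDAS assessments after the gap and does not flare.

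Table 3.3 has a row headed "Subject with Missing ASDAS at two consecutive visits", which reads censored under the observed case and does not show the exception. Section 3.2.22, in the rule for the main approach, foresees that some subjects come back: a gap counts as a flare there "even if ASDAS scores are available after the missed visits".

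Section 8.2.2.1 repeats the Kaplan-Meier estimates and the stratified log-rank test under this definition. The estimates are given by arm at twelve time points from Week 52 to Week 96.

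**The concern.** Kaplan-Meier and log-rank methods require that censoring does not depend on the event still to come. Here it does. Take two subjects with the same gap who both resume visits. The one who later flares is counted as an event. The one who is later seen to be flare-free is removed at the second missed visit, and the flare-free ASDAS values observed after that visit are discarded. Returning flarers stay in the analysis and returning non-flarers leave it, so the reported flare percentages are too high. An analysis named observed case should not drop observed follow-up because of its result.

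What is at stake is the accuracy of the by-arm flare percentages in one sensitivity analysis of a secondary endpoint. It is one of the analyses a reader would use to see how far the time-to-flare result depends on counting missing data as flares.

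**Working it through.** **The plan's own figure.** The SAP states no figure for this analysis. The nearest is the power in section 2.4, which supplies the flare rates used below. With 70 subjects per arm, two-sided 0.05 and no-flare proportions of 80%, 75% and 45%, the pooled normal approximation gives 99.4% and 96.0%. Fisher's exact test gives 98.9% and 94.0%. The SAP states 98% and 94%. The inputs are therefore read correctly, and the point does not depend on the power.

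**Direction.** The Kaplan-Meier flare proportion is 1 − ∏(1 − d_j/n_j), with d_j events and n_j subjects at risk at event time j. Compare the SAP rule with keeping every returning subject at risk, and date later flares at the qualifying ASDAS. The d_j and the event times are identical. The n_j are equal or smaller under the SAP rule, because returning non-flarers have left. Each factor is then equal or smaller, and the flare proportion equal or higher.

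**Small example.** Ten subjects, four of whom miss Weeks 56 and 60 and return at Week 64. Two of those four flare at Week 72 and two never do. Of the other six, three flare at Week 72 and three never do.
- SAP rule: the two returning non-flarers leave at Week 60, so 5/8 = 62.5%.
- Keep all returning subjects at risk: 5/10 = 50%.
- Censor all four at Week 60: 3/6 = 50%.
- SAP rule with later flares dated instead at the second missed visit: 1 − (8/10)(3/6) = 60%.

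**Size.** Large-sample simulation with 400,000 subjects per arm. Flare times are exponential, matched to 20%, 25% and 55% flaring (the complements of section 2.4). ASDAS visits are at Weeks 50 and 52, then every 4 weeks to Week 92. A two-visit gap is placed at random, unrelated to flare, with return at the next visit. The gap shares are assumptions and are the shares assigned; some subjects flare before their gap, so a 10% share leaves 9.2%, 9.0% and 7.6% with an actual gap. Each cell gives the flare percentage by Week 96 under the SAP rule, then with all returning subjects kept at risk, then the difference in points.

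| Gap share | CZP Q2W | CZP Q4W | PBO |
|---|---|---|---|
| 2% | 20.2 / 20.0 / 0.2 | 25.1 / 25.0 / 0.1 | 55.4 / 55.1 / 0.3 |
| 5% | 20.4 / 20.0 / 0.4 | 25.5 / 25.0 / 0.5 | 55.7 / 55.0 / 0.7 |
| 10% | 20.8 / 20.0 / 0.8 | 25.9 / 24.9 / 1.0 | 56.4 / 55.1 / 1.3 |

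Against the input value of 55.0%, the PBO difference at 2% is 0.4 points. If later flares are dated at the second missed visit, the 10% row is unchanged at 20.8%, 25.9% and 56.4%.

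**Between arms.** With 70 per arm, Q2W against PBO, equal gap shares of 10% and 1,500 replicates, the mean log-rank z is −4.30 under the SAP rule and −4.33 with all returning subjects kept at risk. The simulated test is unstratified; the planned one is stratified by region and mNY classification.

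**Scale.** Gap shares of 2%, 5% and 10% are 1.4, 3.5 and 7 of 70 subjects. The sampling standard error of a 55% flare proportion in 70 subjects is √(0.55 × 0.45/70) = 5.9 points.

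**The case against.** The strongest reply is that the affected group is nearly emptied by design. Section 3.6.9 lists two consecutive missing ASDAS scores among the IXRS flare criteria, and section 5.1 shows that IXRS moves flared subjects to the Escape Part. Section 3.1 keeps post-flare assessments of subjects who start escape out of Part B summaries, and section 4.2 treats post-flare efficacy data as missing. Section 3.2.22 narrows the group further: an unscheduled ASDAS not above 3.5 between the two missed visits cancels the gap. This stands as a limit on size. It does not remove the defect, since the rule is written for exactly the subjects who remain.

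A second reply is that a returning subject who completes Part B without a flare also fits the Table 3.3 row for no-flare completers, censored at Week 96. On that reading the bias would not arise for that subject. But the text of 3.2.23 censors at the gap and makes an exception only for later flarers, and the table does not say which row takes precedence. This is a reason to settle the wording.

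A third reply is that the flare date for later flarers could mean the second missed visit, because the main rule dates gap flares there. Those subjects would then not keep their later risk time. The estimate is still too high, as shown above.

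A reader might also infer that the comparison of CZP with PBO is distorted, since the bias in points is larger where flares are commoner. The working does not support that when gap rates are equal: the log-rank statistic hardly moves, and the small shift is against CZP.

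**Conclusion.** The point holds as a defect in the censoring rule of one sensitivity analysis. The upward direction follows from the rule; the size does not follow from the SAP, which gives no gap rate. At assumed gap shares of 2%, 5% and 10%, unrelated to flare and followed by return to Part B follow-up, the overstatement is about 0.1 to 0.4, 0.4 to 0.7 and 0.8 to 1.3 points. The IXRS criterion makes the low end more likely. All of these are well below the sampling error of one arm.

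A reader might infer a wider consequence, but the SAP does not support it. The primary analysis is not affected: there, two missing scores count as a flare for everyone. The observed-case version of the primary endpoint (3.2.22.1) does not contain this censoring rule. The time-to-flare p-values are nominal (sections 4.5 and 8.2.2), and time to flare has a second sensitivity approach, the alternative handling of premature withdrawal. Unequal gap rates between arms could matter more; that case was not quantified.

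**What to change.** In the observed-case part of 3.2.23, apply one rule whatever happens later:
- A subject who resumes ASDAS assessments after a gap and has not started escape stays at risk. If the subject later flares, the event is at the date of the qualifying ASDAS. Otherwise the subject is censored at the last available pre-escape ASDAS, or at Week 96 if Part B is completed.
- Censor at the gap only subjects with no later pre-escape ASDAS.
- State outright that the flare date for later flarers is the qualifying ASDAS date, in place of the reference back to the rest of the section.
- In Table 3.3, align the row for two missing scores and the row for completers without a flare, so that each subject fits one row.

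Censoring every gap subject and ignoring later flares would also be uniform, but it should not be used. It discards observed flares, against the section's own event definition and the first two rows of Table 3.3. Censoring everyone at the second missed visit also understated the PBO flare percentage in the simulation (54.3% against 55.1% at a 10% gap share).

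The cost is a few sentences in 3.2.23, one change to the censoring derivation and two table rows. No new data are needed.

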#### Alternative handling of premature withdrawal

In this approach, a different handling of subject experiencing premature withdrawal from Part B at any point will be considered. Only subjects with a primary reason for premature withdrawal recorded as “adverse event” or “lack of efficacy” will be considered as having a flare. The other subjects experiencing premature withdrawal from Part B will not be considered as having a flare (unless other flare criteria are met).

Consequently, subjects with a primary reason for premature withdrawal recorded as “adverse event” or “lack of efficacy” will be treated as having experienced a flare at the date of their Withdrawal Visit. The other subjects experiencing premature withdrawal from Part B will not be considered as having a flare (unless other flare criteria are met) and will be censored at the date of their Withdrawal Visit.

Overview of different approaches for flare definition:

**Table 3.3: Flare Definition and Time to Flare**

Reason for flare	Event/Censoring day	Non-responder imputation	Observed Case	Alternative handling of premature withdrawal
ASDAS >=2.1 at 2 consecutive visits	Day of 2nd ASDAS	Event	Event	Event
ASDAS >3.5	Day of ASDAS	Event	Event	Event
Subject with Missing ASDAS at two consecutive visits	Planned date for the 2nd ASDAS visit	Event	Censored	Event
Subject discontinued study during Part B due to AE or Lack of efficacy	Day of discontinuation not equal ASDAS visit	Event	Censored	Event
Subject discontinued study during Part B due to other reason	Day of discontinuation not equal ASDAS visit	Event	Censored	Censored
No Flare (completed Part B)	Week 96	Censored	Censored	Censored
Incorrectly 'flared' due to delay in data entry	2nd ASDAS visit or planned date for the 2nd ASDAS visit if missing	Event	Censored	Censored

**3.2.24 Subject age**

Age in years will be calculated in the Study Data Tabulation Model (SDTM) data using the methodology defined in the UCB Interpretation of the SDTM Implementation Guide. For subjects with partial dates of birth (DOB), age will be calculated using the imputed DOB as provided by data management (DM). The imputation of partial DOBs by DM will be based on UCB data management standards.

**3.2.25 Subject race**

All subjects enrolled at French sites will not provide race data. Even in the case such data was provided by the sites in error, it will be ignored for tables and only presented in listings.

**3.2.26 Anti-CZP antibody status**

Determination of ADA will be done using a validated screening, confirmation, and titration ADA bridging assay. The immunogenicity data will be analyzed according to dedicated Bioanalytical Analysis plans.

**3.2.27 Modified New York criteria**

Subjects will be defined as having radiographic axial spondyloarthritis (r-axSpA) or non-radiographic axial spondyloarthritis (nr-axSpA) in this study based solely on the radiologic criterion. For simplification, r-axSpA will be referred to AS in the SAP and statistical outputs. If

a subject has sacroiliitis grade  $\geq 2$  bilaterally or sacroiliitis grade 3 to 4 unilaterally on x-ray then the subject will be considered to have AS/be modified New York (mNY) positive, otherwise they will be considered to have nr-axSPA/be mNY negative.

The mNY classification will be determined at Screening. MRI will be assessed centrally and by 2 independent readers. If the results from the readers are different, then the result of the adjudicator will be used as the adjudicator's decision was considered final for the inclusion of the subject in the study. If the modified NY criteria data recorded in the 'Modified NY Criteria for Ankylosing Spondylitis' eCRF differs from the MRI result reported by central review, the result from central review will be used in summary table instead of the result reported in the eCRF.

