### 3.2.12 Maastricht Ankylosing Spondylitis Enthesitis Score (MASES)

The MASES comprises 13 items (bilateral costochondral 1, costochondral 7, anterior superior iliac spine, posterior iliac spine, iliac crest and proximal insertion of the Achilles tendon sites, and the fifth lumbar vertebral body spinous process) (Heuft-Dorenbosch et al, 2003) each scored as 0 = yes or 1 = no and then summed for a possible score of 0 to 13, with higher scores indicating worse enthesitis.

If 7 or more items are available, MASES will be imputed by dividing the sum score with the number of assessments and multiplying the result with 13. If less than 7 items are available, MASES will be treated as missing.

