### **3.2.20      Inflammatory Bowel Disease Questionnaire (IBD-Q)**

The IBD-Q is a validated quality of life questionnaire, which combines an assessment of symptoms as a result of IBD, the way the subject has been feeling in general, and how their mood has been over the previous 2 weeks.

The IBD-Q contains 32 questions covering 4 domains of subjects' lives (bowel symptoms, systemic symptoms, emotional function, and social function).

Subjects will be asked to answer questions relating to the impact of their CD on their HRQoL over the 2 weeks prior to their study visit using the IBD-Q. The IBD-Q must be completed by the subject prior to start any study-related activities.

The method as detailed by Guyatt et al, 1989 will be used in the calculation of the IBD-Q score.

The total IBD-Q global score will be derived as the sum of the responses (from 1 to 7) to all 32 questions on the IBD-Q and can therefore range from 32 to 224. The IBD-Q score for each of the four categories (bowel symptoms, systemic symptoms, emotional function and social function) will be defined as the sum of the responses of the subset of questions of the IBD-Q as specified below:

- Bowel Symptoms Questions 1, 5, 9, 13, 17, 20, 22, 24, 26, 29
- Systemic Symptoms Questions 2, 6, 10, 14, 18
- Emotional Function Questions 3, 7, 11, 15, 19, 21, 23, 25, 27, 30, 31, 32
- Social Function Questions 4, 8, 12, 16, 28.

An IBD-Q response is defined as a clinically meaningful improvement in the total IBD-Q global score and corresponds to an increase in the total IBD-Q global score  $\geq 16$  points from Baseline. IBD-Q remission is defined as a total IBD-Q global score  $\geq 170$  points.

The following approach will be applied in the case of partially completed questionnaires.

The IBD-Q score for the four categories (bowel symptoms, systemic symptoms, emotional function and social function) will be calculated if only, at maximum, one of the items responses within the category is missing. The IBD-Q category score will be imputed by dividing the sum score with the number of available items responses and multiplying the result by the number of completed items within the category. If two or more items responses are missing within a category, the corresponding IBD-Q category score will be left missing.

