## **4 STATISTICAL/ANALYTICAL ISSUES**

### **4.1 Adjustments for covariates**

The randomization stratification factors of geographical region and the mNY criteria as defined in Section 3.2.27 will be used as covariates in the specified statistical models. The original values of the stratification factors used at the time of randomization will be recorded into IXRS. Of note in case any errors to the stratification factors is detected, no updates will be done to the IXRS data. However, the correct values of the stratification factors (including any corrections post randomization) will be used for the analyses.

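### Three derivation rules in SAP Section 3.2 fail as written: IBD-Q domain prorating imputes nothing, MASES items are coded in reverse, and x-ray-based mNY status is given an MRI read and override

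*SAP*

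**What the plan says.** **IBD-Q domains (SAP 3.2.20).** A domain is scored if no more than one of its items is missing. The sum is divided by the count of available answers, followed by "multiplying the result by the number of completed items within the category". Items run from 1 to 7. The listed domains have 10 (bowel), 5 (systemic), 12 (emotional) and 5 (social) items. The global score is prorated separately, to 32 items.

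**MASES (SAP 3.2.12).** The 13 sites are "each scored as 0 = yes or 1 = no and then summed for a possible score of 0 to 13", and the same sentence says that a higher score means worse enthesitis. If at least 7 sites are assessed, the sum is prorated to 13.

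**mNY status (SAP 3.2.27).** Radiographic or non-radiographic disease is decided "in this study based solely on the radiologic criterion", that is, by grade 2 or higher sacroiliitis "bilaterally or sacroiliitis grade 3 to 4 unilaterally on x-ray then the subject will be considered to have AS/be modified New York (mNY) positive". The next paragraph places the classification at Screening but then states that "MRI will be assessed centrally and by 2 independent readers", with an adjudicator if they disagree. It closes with a rule for mNY eCRF data: where that entry "differs from the MRI result reported by central review, the result from central review will be used in summary table".

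**Use of mNY (SAP 4.1).** "The randomization stratification factors of geographical region and the mNY criteria as defined in Section 3.2.27 will be used as covariates". Section 8.1.1 specifies the final values of the stratification factors for the primary model.

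**The concern.** A programmer who codes these three rules literally gets a wrong value or cannot follow the text.

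- The IBD-Q domain rule looks like prorating but has no effect. An item missing at one visit only would appear as a change in quality of life.
- The MASES coding contradicts the direction given in its own sentence. Coded literally, an improvement in enthesitis would be reported as a worsening.
- The mNY section defines status by one imaging modality and describes reading, adjudication and override for another. MRI does not yield an x-ray sacroiliitis grade; the two MRI scores in Section 3.2.4 grade bone marrow edema. The eCRF mNY data in the summary table could therefore be replaced by a result that does not measure the criterion.

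**Working it through.** **1. IBD-Q domain with one missing item.** Let k be the number of items in the domain and S the sum of the k − 1 answers given.

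- As written: S / (k − 1) × (k − 1) = S. Available and completed items are the same count, so the missing item contributes 0, below the item minimum of 1.
- Prorated to the full domain: S / (k − 1) × k.
- The written score is (k − 1)/k of the prorated score, a shortfall of 1/k. With equal item answers the prorated score is also the complete score.

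| Domain | k | Written, all answers 5 | Prorated | Shortfall 1/k |
|---|---|---|---|---|
| Bowel | 10 | 45 | 50 | 10% |
| Systemic | 5 | 20 | 25 | 20% |
| Emotional | 12 | 55 | 60 | 8.3% |
| Social | 5 | 20 | 25 | 20% |

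A 5-item domain answered 1 throughout with one item missing scores 4, below the lowest possible value of 5. A stable subject answering 5 throughout, with one systemic item missing at follow-up only, shows a change of 20 − 25 = −5.

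The item lists cover questions 1 to 32 once each (10 + 5 + 12 + 5 = 32), which agrees with the stated global range of 32 to 224. With one item missing in every domain and all answers 5, the global rule gives 140 / 28 × 32 = 160, while the four domains as written add to 45 + 20 + 55 + 20 = 140. The plan's other prorating rules all multiply by the full item count: ASQoL by 18 (3.2.8), MASES by 13 (3.2.12), joint counts by 44 (3.2.13) and the IBD-Q global score by 32.

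**2. MASES.** Assume that yes means enthesitis present at the site. With t affected sites out of 13, the written score is 0 × t + 1 × (13 − t) = 13 − t.

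| Affected sites | Written score | Score with yes = 1 |
|---|---|---|
| 0 | 13 | 0 |
| 3 | 10 | 3 |
| 7 | 6 | 7 |
| 13 | 0 | 13 |

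Prorating does not repair this. With 10 sites assessed and 2 affected, the written rule gives 8/10 × 13 = 10.4 and the reversed coding 2/10 × 13 = 2.6. For change, (13 − t₂) − (13 − t₁) = −(t₂ − t₁), so the sign flips.

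**3. mNY status.** No arithmetic applies; the parts of 3.2.27 are set side by side.

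| Element | Modality named |
|---|---|
| Definition of mNY positive | X-ray grade, and nothing else |
| Central reading by two readers, with adjudication | MRI |
| Override of the eCRF mNY data | MRI, for the summary table |

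The definition excludes MRI, while the reading and override sentences name only MRI. No rule converts an MRI result into an mNY grade. Section 3.2.28 has a similar central-review override for the modified ASAS criteria, where MRI is one of the items named; there it causes no conflict.

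**The case against.** The best reply is that these are visible slips with limited reach. Most of that stands.

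- **IBD-Q.** Only domain scores with exactly one missing item are affected, and they are summarized descriptively (8.3.1.20, 8.3.2.12, 8.3.3). Response, remission and the correlations use the global score, which is prorated correctly.
- **MASES.** The item question is not given, so the meaning of yes is inferred. Range, direction and prorating are stated properly, and MASES is descriptive only (8.3.1.14, 8.3.2.12, 8.3.3). Still, no other reading of yes suits an enthesitis count.
- **mNY.** The word MRI may simply stand for another central read, and the override is confined to a summary table; Section 6.2 plans a table of the mNY criteria.

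A reader might infer that the MRI override also changes the covariate in the primary logistic model, the log-rank strata, the subgroups and every AS / nr-axSpA column. The SAP does not show this. Section 4.1 points to the criteria as defined in 3.2.27, and the only definition there is the x-ray grade. Sections 4.1 and 8.1.1 call for corrected or final stratification values without saying that they come from MRI. Moreover, mNY status is fixed at Screening, before randomization, so an error in it would not depend on treatment arm.

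A reader might also want to estimate how many subjects would be misclassified. That needs the share with non-radiographic disease, the share of those who are MRI-positive, and a rule turning MRI into mNY status. The SAP gives none of these.

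**Conclusion.** The three passages need correction.

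- The IBD-Q domain rule is wrong by algebra. It understates an affected domain by 20%, 10% or 8.3%, assuming equal item answers, and only when exactly one item is missing.
- The MASES coding reverses the score and the sign of its change, assuming that yes means enthesitis present.
- Section 3.2.27 contradicts itself on modality. As written, a central MRI result replaces x-ray-based mNY data in the summary table. Its effect cannot be sized from the SAP, and no effect on the covariate or strata is shown.

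The sample size and significance level are untouched, and no effect on the primary analysis is shown. The mNY text still deserves an explicit statement, because the same section supplies the definition of a covariate in the primary model.

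**What to change.** 1. **Section 3.2.20:** multiply the mean of the available answers by the total number of items in the category: 10 (bowel), 5 (systemic), 12 (emotional), 5 (social).
2. **Section 3.2.12:** score each site 1 = yes (enthesitis present) and 0 = no.
3. **Section 3.2.27:** make the reader, adjudication and override sentences refer to the central read of the sacroiliac x-ray, if one was done. The SAP does not describe such a read; if there was none, delete the override. State that an MRI result does not set mNY status, and that the model covariate and the strata use the x-ray-based value.

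The cost is three wording corrections and a check that the derivation programs follow them. No new data are needed.
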